NON-INTERVENTIONAL (NI) STUDY PROTOCOL

Study information

[figure not shown]
Title	Patient profiles and treatment patterns among ALK+ NSCLC patients treated with alectinib.
Protocol number	B7461031
Protocol version identifier	2.0
Date	31 August 2021
Research question and objectives	This study aims to understand patient profiles, treatment patterns, and clinical outcomes among ALK+ NSCLC patients treated with alectinib, and post-alectinib treatment patterns and outcomes.
	Phase 1 Landscape Objectives (structured data):
	These analyses will be performed for all study-eligible patients who received alectinib during the study identification period. Results will be presented overall as well as for the subgroups of patients who received a subsequent therapy following alectinib:
	1. Describe the demographic and clinical characteristics of ALK+ NSCLC patients who received alectinib overall, and stratified by subsequent treatment following alectinib.
	2. Characterize post-alectinib treatment patterns and sequencing of other ALK inhibitors; categorizing type of treatments received after alectinib.

- 3. Estimate duration of therapy with alectinib and duration of therapy for post-alectinib treatment.
- 4. Examine overall survival of patients postalectinib stratified by subsequent treatment following alectinib.

Phase 2: Chart Review Objectives (unstructured data):

For Phase 2, structured data will be supplemented with a targeted chart review to confirm alectinib and other ALK inhibitor oral drug therapy information and collect additional unstructured data for a sample of front-line alectinib patients from the eligible study population. Results will be presented for all patients selected for chart review, as well as the subgroups of patients who received a subsequent therapy following alectinib:

- 5. Describe the demographic and clinical characteristics of ALK+ NSCLC patients who received alectinib overall, and stratified by subsequent treatment following alectinib.
- 6. Characterize post-alectinib treatment patterns and sequencing of other ALK inhibitors; categorizing type of treatments received after alectinib.
- 7. Estimate duration of therapy with alectinib and duration of therapy for post-alectinib treatment.
- 8. Examine reasons for treatment discontinuation of alectinib and post-alectinib treatment.

PPD
Phone: PPD Email: PPD

2. LIST OF ABBREVIATIONS

Abbreviation	Definition		
AE	adverse event		
AEM	adverse event monitoring		
ALK	anaplastic lymphoma kinase		
ANOVA	analysis of variance		
BRAF	v-raf murine sarcoma viral oncogene homolog B1		
CI	confidence interval		
CNS	central nervous system		
CRFs	case report forms		
DCTs	data collection tools		
DOT	duration of treatment		
ECOG	Eastern Cooperative Oncology Group		
eCRF	electronic case report form		
EGFR	epidermal growth factor receptor		
EHR	electronic health record		
EMA	European Medicines Agency		
ENCePP	European Network of Centers for Pharmacoepidemiology and Pharmacovigilance		
FDA	Food and Drug Administration		
FISH	fluorescence in situ hybridization		
GEP	good epidemiological practice		
GPP	guidelines for good pharmacoepidemiology Practices		

Abbreviation	Definition	
HIPAA	health insurance portability and accountability act	
НІТЕСН	health information technology for economic and clinical health	
HR	hazard ratio	
ICD	international classification of diseases	
ICMJE	international committee of medical journal editors	
IHC	Immunohistochemistry	
iKM	iKnowMed	
IEA	International Epidemiological Association	
IEC	Independent Ethics Committee	
IRB	Institutional Review Board	
ISPE	International Society for Pharmacoepidemiology	
K-M	kaplan meier	
LADMF	limited access death master file	
MET	mesenchymal-to-epithelial transition	
MRN	medical record number	
NI	non-interventional	
NIS	non-interventional study	
NOS	not otherwise specified	
NSCLC	non-small cell lung cancer	
OS	overall survival	
PD-L1	programmed death-ligand 1	

Abbreviation	Definition	
PFS	progression free survival	
QC	quality control	
RECIST	response evaluation criteria in solid tumors	
ROS1	ROS proto-oncogene 1	
RT-PCDR	reverse transcriptase– polymerase chain reaction	
SSDI	social security death index	
SSN	social security number	
US	United States	
YRR	your reporting responsibilities	

4. ABSTRACT

Title: Patient profiles and treatment patterns among anaplastic lymphoma kinase (ALK)-positive non-small cell lung cancer (NSCLC) patients treated with alectinib.

Version and Date of Protocol: 2.0 31 August 2021

Main Author: PPD , PhD, Pfizer Inc; PPD , PhD, Ontada

Rationale and background:

Alectinib is a second-generation kinase inhibitor indicated for the treatment of patients with ALK+ metastatic NSCLC. Alectinib was first FDA approved in December 2015 for the treatment of ALK+ NSCLC in patients following treatment with the first generation ALK inhibitor crizotinib. In November of 2017, the FDA approved alectinib for use as first-line treatment for ALK+ metastatic NSCLC.

The approval was based on the Phase 3 ALEX trial of 303 first-line ALK+ NSCLC patients. Treatment with alectinib demonstrated a significantly reduced risk of progression or death by 47 percent (HR=0.53, 95 percent CI: 0.38, 0.73, p<0.0001) compared to crizotinib. Median PFS was 25.7 months (95 percent CI: 19.9, not estimable) for patients treated with alectinib compared with 10.4 months (95 percent CI: 7.7, 14.6) for patients who received crizotinib. Treatment with alectinib also reduced the risk of the brain or central nervous system (CNS) metastasis compared to crizotinib by 84 percent (HR=0.16, 95 percent CI: 0.10, 0.28, p<0.0001).[1]

With the availability of several therapeutic agents, current treatment patterns and outcomes with use of multiple ALK-inhibitor treatments in sequence are not well understood. For patients with ALK positive NSCLC, first-line therapy with alectinib is the preferred treatment option, however, sequence of therapy is not well-defined. This study aims to understand patient profiles, treatment patterns, and clinical outcomes among ALK+ NSCLC patients treated with alectinib, and post-alectinib treatment patterns and outcomes.

Research question and objectives

Describe patient profiles, treatment patterns, and clinical outcomes among real-world ALK+ NSCLC patients treated with alectinib, and post-alectinib treatment patterns and outcomes.

Specifically, we will answer the following objectives:

Phase 1: Landscape Objectives (structured data):

These analyses will be performed for all study-eligible patients who received alectinib (in any line of therapy) during the study identification period. Results will be presented overall as well as for the subgroups of patients who received a subsequent therapy following alectinib:

- 1. Describe the demographic and clinical characteristics of ALK+ NSCLC patients who received alectinib overall, and stratified by subsequent treatment following alectinib
- 2. Characterize post-alectinib treatment patterns and sequencing of other ALK inhibitors; categorizing type of treatments received after alectinib
- 3. Estimate duration of therapy with alectinib and duration of therapy for post-alectinib treatment
- 4. Examine overall survival of patients post-alectinib stratified by subsequent treatment following alectinib

Phase 2: Chart Review Objectives (unstructured data):

For Phase 2, structured data will be supplemented with a targeted chart review to confirm alectinib and other ALK inhibitor oral drug therapy information and collect additional unstructured data for a sample of front-line alectinib (i.e., first treatment administration of alectinib not preceded by any other product for NSCLC therapy) patients, from the eligible study population. Results will be presented for all patients selected for chart review, as well as the subgroups of patients who received a subsequent therapy following alectinib:

- 5. Describe the demographic and clinical characteristics of ALK+ NSCLC patients who received alectinib overall, and stratified by subsequent treatment following alectinib
- 6. Characterize post-alectinib treatment patterns and sequencing of other ALK inhibitors; categorizing type of treatments received after alectinib
- 7. Estimate duration of therapy with alectinib and duration of therapy for post-alectinib treatment
- 8. Examine reasons for treatment discontinuation of alectinib and post-alectinib treatment
- 9. Estimate progression-free survival (PFS) of patients post-alectinib stratified by subsequent treatment (as supported by the final sample size)
- 10. Examine overall survival of patients post-alectinib stratified by subsequent treatment (as supported by the final sample size)

Phase 3: Data Refresh (structured and unstructured data) and exploratory analysis (structured data)

For Phase 3, the structured and unstructured data study objectives (Phase 1 and Phase 2) will be updated with additional follow-up time through 31 August 2021.

In addition, patients initiating lorlatinib following FDA approval to end of study period will be identified in structured data and the following exploratory objectives will be examined:

- 11. Identify patients initiating lorlatinib and monitor lorlatinib uptake over time
 - Evaluate demographic and clinical characteristics of patients receiving lorlatinib
 - Characterize lorlatinib treatment sequencing utilization and patterns

Study design: This is a retrospective, observational, descriptive study to examine patient characteristics, treatment patterns, and outcomes of patients ALK+ NSCLC treated in The United States (US) Oncology Network and Non-Network practices utilizing the iKnowMed (iKM) electronic healthcare record (EHR).

Population: The study population will consist of patients with a diagnosis of NSCLC receiving alectinib within in The US Oncology Network and Non-Network practices.

Study Population

The study population for Phases 1 and 2 will be comprised of ALK+ NSCLC patients who have evidence of receiving alectinib during 01 June 2017 and 30 June 2019 with The US Oncology Network or Non-Network site. Study-eligible patients will be followed longitudinally until 31 December 2019, last patient record or date of death, whichever occurs first. The index date-1 will be the start date of alectinib treatment during the study identification period. Index date-2 will be the start date of the subsequent treatment following alectinib, among patients who receive a next treatment.

For Phase 3, the identification period for the study population will be extended to include ALK+ NSCLC patients who have evidence of receiving during 01 June 2017 and 31 August 2020 with The US Oncology Network or Non-Network site. Study-eligible patients will be followed longitudinally with additional follow-up until 31 August 2021, last patient record or date of death, whichever occurs first. The index date-1 will be the start date of alectinib treatment during the study identification period. Index date-2 will be the start date of the subsequent treatment following alectinib, among patients who receive a next treatment during the study identification period. For the lorlatinib exploratory analysis the identification period will be 02 November 2018 to 31 August 2020. Study-eligible patients will be followed longitudinally with additional follow-up until 31 August 2021, last patient record or date of death, whichever occurs first.

Variables: A complete list of study variables and their associated operational definition are presented in Table 1.

Data Sources: Structured data fields within the iKM EHR database will provide information needed to address most research questions. These data will be supplemented by additional unstructured data collected through chart review for a subset of the study population.

Study size

A preliminary feasibility assessment for Phases 1 and 2 identified 293 patients who were treated with alectinib after 01 November 2017, with approximately half treated in the front-line setting. Approximately 20-30% of these patients received a subsequent therapy after alectinib. It is estimated that approximately 300 patients will be included in the Phase 1 structured data analysis. Targeted chart review for Phase 2 is proposed to occur on 150 patients receiving alectinib to identify at least 100 patients who received alectinib as front-line.

For Phase 3 structured analysis, a preliminary feasibility assessment identified 521 patients who were treated with alectinib from 01 June 2017 through 31 December 2020. Chart review for Phase 3 will include patients who had ongoing treatment at the end of Phase 2 study period, and an additional 125 patients will be targeted to identify 100 new patient who received alectinib as front-line therapy. For Phase 3 exploratory analysis, a preliminary feasibility assessment identified 134 patients who were treated with lorlatinib from 01 November 2018 through 31 December 2020.

The final study population for analysis will be defined after identification and review of the patient population meeting the eligibility criteria in the iKM database. A specific power calculation will not be performed as this is a descriptive analysis.

Data analysis

Descriptive analyses will be conducted to evaluate demographic, clinical and treatment characteristics overall, as well as for each of the study cohorts. Time-to-event outcomes (OS, DOT, PFS) will be assessed using the Kaplan-Meier method with 95% CIs and summary tables. All analyses will be presented for each of the study cohorts and, as supported by the final sample size, stratified by front-line alectinib and non front-line alectinib treatment groups.

Milestones

Interim reports for Phase 1 are expected to be delivered May 2020, with the final study report expected October 2020.

The final report for Phase 3 is expected to be delivered in March 2022.

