7. RATIONALE AND BACKGROUND

Lung cancer is the second most common cancer in the United States (US) with approximately 235,760 new lung cancer diagnoses estimated to occur in 2021 with 131,880 deaths during this time.[2] Worldwide, lung cancer is a predominant cause of cancer related mortality as the disease is usually diagnosed late. At the initial diagnosis, almost 70% of patients with lung cancer either have a locally advanced disease or have distant metastases. The median overall survival (OS) from diagnosis for patients with stage IV anaplastic lymphoma kinase (ALK)-positive non-small cell lung cancer (NSCLC) is 6.8 years. [3]

Lung cancer is of mainly 2 types, small cell lung cancer and non-small cell lung cancer (NSCLC). These 2 subtypes are treated differently through different chemotherapy and radiotherapy regimens. NSCLC comprises around 85-90% of all lung cancers with 40% of these having adenocarcinoma histology. This type of lung cancer occurs mainly in current or former smokers, but it is also the most common type of lung cancer seen in non-smokers. It is more common in women than in men, and it is more likely to occur in younger people than other types of lung cancer. [4]

A genetic alteration of the anaplastic lymphoma kinase (ALK) gene is present in 3-5% of NSCLCs. Over the last decade, there has been an increase in the number of oral anticancer agents available for use as treatment. The availability of orally available cancer treatments has made it possible for patients to receive their treatments without having to travel long distances. [5]

Biomarker driven therapies have revolutionized the treatment of non-small cell lung cancer (NSCLC). The first FDA-approved ALK inhibitor for ALK+ (ALK+) metastatic NSCLC treatment in 2011, crizotinib, has shown significant improvement in progression-free survival (PFS) and tumor responses in patients with metastatic NSCLC who carry the ALK gene rearrangement. While crizotinib has demonstrated significant improvement in PFS in Phase 3 studies, a subset of patients may develop acquired resistance to the drug after approximately 12 months, most likely due to secondary mutations to the ALK gene. [6-15]

For patients who progress on crizotinib, second generation ALK-inhibitors have been developed. Additional ALK-inhibitors that have subsequently been approved include ceritinib (April 2014), alectinib (December 2015), and brigatinib (April 2017).

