Alectinib is a second-generation kinase inhibitor indicated for the treatment of patients with ALK+ metastatic NSCLC. Alectinib was first FDA approved in December 2015 for the treatment of ALK+ NSCLC in patients following treatment with the first generation ALK inhibitor crizotinib. In November of 2017, the FDA approved alectinib for use as first-line treatment for ALK+ metastatic NSCLC.

The approval was based on the Phase 3 ALEX trial of 303 first-line ALK+ NSCLC patients. Treatment with alectinib demonstrated a significantly reduced risk of progression or death by 47 percent (HR=0.53, 95 percent CI: 0.38, 0.73, p<0.0001) compared to crizotinib. Median

PFS was 25.7 months (95 percent CI: 19.9, not estimable) for patients treated with alectinib compared with 10.4 months (95 percent CI: 7.7, 14.6) for patients who received crizotinib. Treatment with alectinib also reduced the risk of the brain or central nervous system (CNS) metastasis compared to crizotinib by 84 percent (HR=0.16, 95 percent CI: 0.10, 0.28, p<0.0001).[1]

Likewise, ceritinib (Zykadia®), has been tested in the frontline setting. In the ASCEND-4 Phase 3 trial, ceritinib was compared to a platinum/pemetrexed demonstrating a median progression free survival of 16.6 months as compared to only 8.1 months in the platinum/pemetrexed chemotherapy arm. Other comparisons of second and third generation ALK inhibitors to ceritinib are ongoing.[16]

More recently, in November 2018, the FDA granted accelerated approval to lorlatinib for patients with ALK+ metastatic NSCLC whose disease has progressed on crizotinib and at least one other ALK inhibitor or whose disease has progressed on alectinib or ceritinib as the first ALK inhibitor therapy.[17] The accelerated FDA approval was converted to a full approval and the indication was expanded to include first-line treatment for patients with ALK+ metastatic NSCLC in March 2021. [18]

With the availability of several therapeutic agents, current treatment patterns and outcomes with use of multiple ALK-inhibitor treatments in sequence are not well understood. For patients with ALK positive NSCLC, first-line therapy with alectinib is the preferred treatment option, however, sequence of therapy is not well-defined. This study aims to understand patient profiles, treatment patterns, and clinical outcomes among ALK+ NSCLC patients treated with alectinib, and post-alectinib treatment patterns and outcomes.

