9.3.3. Cohort definitions and stratifications

Separate study cohorts will be considered in all phases of the project.

For Phase 1, results will be presented for all patients who meet study eligibility criteria listed in Section 9.3.1 and stratified by subsequent treatment following alectinib (as described in Section 9.1).

For Phase 2, a sample of patients who received alectinib as front-line therapy (i.e., first treatment administration of alectinib not preceded by any other product for NSCLC therapy) will be selected for chart review and results will be presented for all patients selected for chart review and stratified by subsequent treatment following alectinib.

For Phase 3, the stratifications for Phases 1 and 2 will be replicated for all patients who meet study eligibility criteria with the extended identification and observation period as outlined in 9.3. An additional sample of patients identified for chart review for Phase 3 will be stratified by the specified subsequent treatment groups specified in 9.3.1.

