Reason for ALK inhibitor (alectinib, and subsequent treatment) treatment discontinuation	Chart review	Treatment characteristics	Study observation period	Data for alectinib and subsequent treatment discontinuation reason will exclusively come from chart review. Reviewers will be asked to select reason(s) as explicitly documented in patients' charts. If available, reason patients discontinued treatment will be abstracted: Completion of therapy Provider-documented disease progression Death Insurance/cost-related Loss to follow-up Patient preference Toxicity Other No information Reviewers will specify other reasons; these will be reported if any represent >5% of patients.	
ALK inhibitor treatment sequencing	iKM structured data + chart review	Treatment pattern	Study observation period	ALK inhibitor treatment paths (e.g. initiate crizotinib followed by ceritinib, initiate crizotinib followed by alectinib, etc.)	
Front-line alectinib	iKM structured data + chart review	Treatment pattern	Study observation period	First treatment administration of alectinib not preceded by any other product for NSCLC therapy except up to 3 months of chemotherapy and immunotherapy preceding alectinib therapy initiation to classify patient as receiving 1L alectinib	
Clinical outcomes					
Last US Oncology Network visit date	iKM structured data + chart review	Clinical outcomes	Study observation period	Each patient's most recent visit date, prior to or on close of study observation period, in the structured data will be recorded. A visit is defined as a physician encounter with the practice where either treatment is given, or vital signs are recorded. For patients with a death date, this last visit date should occur prior to the death date.	

Table 1. Study variables and operational definitions

Variable	Source(s)	Role(s) in study	Period of measurement	Operational definition
				This will not be reported separately; it will be used in calculating the patient's available follow-up time as a descriptive measure. Available follow-up time = Integer (latest of last visit date or death date – index date +1).7

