All descriptive tables will be presented for each of the study cohorts defined above and, as supported by the final sample size, stratified by front-line alectinib and non front-line alectinib treatment groups.

For Phase 3 exploratory objectives, descriptive analyses will be conducted to evaluate the demographic, clinical and treatment characteristics among patients treated with lorlatinib. Results will be reported in aggregate. Categorical variables (e.g., ECOG performance status) will be reported as frequency and percentage. Continuous variables such as age will be reported as mean, standard deviation, median and range (minimum-maximum). In the case of missing observations, the number and percentage of missing values will be reported.

Clinical outcomes

ALK inhibitor DOT, OS, PFS will be assessed using the Kaplan-Meier method with 95% CIs, and summary tables of the number of events and censored patients at 3, 6, 12, 18, and 24 months. Further details about these calculations are presented below and in Table 1.

Clinical outcome results will be presented by study cohort and stratified by front-line alectinib and non-front line alectinib (pending sample size).

Overall survival (OS) will be defined as the interval between start date of alectinib to the date of death as documented in the LADMF and/or iKM EHR database. Patients who did not die will be censored on the study end date or the last visit date available in the database, whichever occurred first. In order to handle censoring, the Kaplan-Meier method will be used to calculate median overall survival with 95% confidence intervals (in number of months). Additionally, 3, 6, 12, 18, and 24-month survival probabilities will be reported. OS will be estimated for the full study population and stratified by study cohort. Log-rank tests will be used to assess statistical differences.

Duration of Therapy (DOT) for ALK inhibitors: An intent to treat approach will be used. DOT will be defined as duration of time (in months) between alectinib treatment initiation and discontinuation, or the last administration date of alectinib, or start date of a subsequent ALK inhibitor, initiation of any subsequent non-ALK inhibitor treatment (as a proxy for evidence of discontinuation), death or check-in in a hospice will be used as a stop date.

There may be some patients who do not have evidence of discontinuation or who do not move on to a subsequent therapy.

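### Structured-data DOT and OS for non-front-line alectinib are not split by prior ALK-inhibitor exposure, and the two front-line definitions disagree on who falls in that stratum

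*Combined protocol and SAP*

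**What the plan says.** Phase 1, and its Phase 3 refresh, takes patients who received alectinib in any line of therapy (Sections 4 and 8). Objectives 3 and 4 report alectinib DOT and OS in that population.

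The Abstract sets the reporting rule: "All analyses will be presented for each of the study cohorts and, as supported by the final sample size", they are also to be "stratified by front-line alectinib and non front-line alectinib treatment groups". Section 9.8.3 repeats it for DOT, OS and PFS: "Clinical outcome results will be presented by study cohort and stratified by front-line alectinib and non-front line alectinib (pending sample size"). The study cohorts A to E are defined by what follows alectinib (Sections 9.1, 9.2 and 9.8.3).

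Front-line is defined in two ways:
- Sections 4, 8 and 9.3.3: "first treatment administration of alectinib not preceded by any other product for NSCLC therapy", with no exception.
- Table 1 (Section 9.4): "not preceded by any other product for NSCLC therapy except up to 3 months of chemotherapy and immunotherapy preceding alectinib therapy initiation".

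Table 1 also has a sequencing variable, "ALK inhibitor treatment paths (e.g. initiate crizotinib followed by ceritinib" being its first example and crizotinib followed by alectinib its second. Section 9.8.3 mentions ALK inhibitor sequences as one example of groups that might be compared, in the part on patient characteristics. Section 9.8 says that no separate statistical analysis plan will be written.

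**The concern.** The protocol's own background treats ALK-inhibitor history as clinically meaningful. Section 7 says of crizotinib that "a subset of patients may develop acquired resistance to the drug after approximately 12 months", and it describes a lorlatinib indication covering patients "whose disease has progressed on alectinib or ceritinib as the first ALK inhibitor therapy". The outcome split is drawn on a different line: whether any NSCLC product came before alectinib, with or without the 3-month tolerance. No DOT or OS analysis is specified by whether an ALK inhibitor came before.

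If the non-front-line stratum holds both kinds of patient, its DOT and OS are a mixture whose value depends on the mix. That mix may change over time: identification opens on 01 June 2017, about five months before the first-line approval of November 2017, when the stated indication was treatment after crizotinib. At stake is whether the any-line estimates for objectives 3 and 4 can be interpreted for patients who already had an ALK inhibitor.

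**Working it through.** The plan states no figure that turns on this point, so there is none to reproduce. The check has three parts.

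**1. Who can be in the non-front-line stratum**

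| History before alectinib | Sections 4, 8, 9.3.3 | Table 1 |
|---|---|---|
| None | Front-line | Front-line |
| Chemotherapy/immunotherapy, up to 3 months | Non-front-line | Front-line |
| Longer non-ALK therapy | Non-front-line | Non-front-line |
| Crizotinib or ceritinib | Non-front-line | Non-front-line |

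Pooling is possible under both definitions. Under Table 1 it is confined to patients with longer prior non-ALK therapy.

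**2. Whether another stratification separates them**

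Cohorts C to E look forward only. Alectinib then lorlatinib, and crizotinib then alectinib then lorlatinib, fall in the same cohort. Crossing the cohorts with the binary split isolates front-line patients and leaves the rest mixed.

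**3. Size**

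The feasibility figures (Sections 4 and 9.6) are 293 patients, about half front-line, so the non-front-line stratum is about 293 × 0.5 = 147. If the half carries over to the Phase 3 count of 521 (an assumption; that count runs to 31 December 2020, past the 31 August 2020 identification cut-off), it is about 521 × 0.5 = 260.

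The documents do not give the naive share f of this stratum, or the ratio r of the naive to the pretreated median. Both are assumed here. With exponential curves and the pretreated median set to 1, the pooled median t solves

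(1 − f) × 0.5^t + f × 0.5^(t/r) = 0.5

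| f | Naive / pretreated, of 147 | Pooled median, r = 1.25 | r = 2.5 |
|---|---|---|---|
| 5% | 7 / 140 | 1.011 | 1.038 |
| 10% | 15 / 132 | 1.022 | 1.080 |
| 20% | 29 / 118 | 1.044 | 1.170 |
| 40% | 59 / 88 | 1.091 | 1.394 |

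Check at f = 20%, r = 2.5: 0.8 × 0.5^1.17 + 0.2 × 0.5^(1.17/2.5) = 0.356 + 0.145 = 0.50.

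The same model in months, with an assumed pretreated median DOT of 8 or 12:
- Naive median 15-18 (assumed), f = 5-10%: pooled median 8.2-8.6 against 8, or 12.1-12.5 against 12. Share on drug at 24 months: 13.5-15.2% against 12.5%, or 25.4-26.5% against 25%.
- Naive median 25.7 (the first-line trial's median PFS in Section 7, a generous proxy for DOT here), f = 40%: pooled median 12.1 against 8, or 15.9 against 12. Share on drug at 24 months: 28.4% against 12.5%, or 35.9% against 25%.

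**The case against.** A reader might infer that the outcome tables fail to answer the ALK-inhibitor sequencing question. The documents do not support that. Objectives 2 and 6 concern treatment after alectinib, and objectives 4 and 10 ask for OS by subsequent treatment. Cohorts C to E serve these, and objectives 3 and 7 include the duration of post-alectinib therapy. No objective asks for outcomes by the ALK inhibitor received before alectinib. Chart review in Phases 2 and 3 is restricted to front-line patients, so those analyses are largely untouched.

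A reader might also take every chemotherapy-then-alectinib patient to be pooled with crizotinib-pretreated patients. Under Table 1 that is not so: those with up to 3 months of prior therapy count as front-line.

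The fix has a data limit as well. Section 9.10.1 says that history before the first network encounter is poorly captured and that drugs from unaffiliated pharmacies are missing, so some pretreated patients would look ALK-inhibitor-naive. Table 1 gives the observation period, which starts on 01 June 2017, as the measurement period of the sequencing variable, so earlier crizotinib could be missed. Even the existing split depends on sample size, in a descriptive study.

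Most of this stands, and it narrows the point. What remains is that DOT and OS in the any-line population have no split by prior ALK inhibitor. The mention of ALK inhibitor sequences in Section 9.8.3 is an example that is not carried into the outcome rules, and no later analysis plan will supply the split. Incomplete history affects the existing front-line split too.

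**Conclusion.** The point holds in a limited form. In the structured-data analyses, non-front-line DOT and OS can mix ALK-inhibitor-naive with ALK-inhibitor-pretreated patients, and the conflict between the two front-line definitions leaves membership of the stratum undetermined.

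The size cannot be derived from the documents. It is small if 5-10% of the stratum is naive (pooled median 1-8% above the pretreated median for r of 1.25 to 2.5) and larger at 40% (9-39%). These figures rest on exponential curves and on assumed values of f and r. A reader might infer that 24-month persistence in pretreated patients is overstated about twofold. That needs the extreme combination of 40% naive with medians of 8 and 25.7 months (28.4/12.5 = 2.3), and nothing in the documents points to it.

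This is an inexpensive improvement to how the objective 3 and 4 estimates can be read. It does not put the study's main objectives in doubt.

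**What to change.** 1. In Sections 4 and 9.8.3, add that structured-cohort DOT and OS will also be reported by alectinib as first versus later ALK inhibitor. If numbers allow, use three groups: front-line; non-front-line with no prior ALK inhibitor; prior ALK inhibitor.
2. Derive prior exposure from Table 1's prior-treatment and sequencing variables, using all available history up to the day before index date-1, and amend their measurement period to match. Section 9.3 already defines such a prior medical history period.
3. Reconcile the front-line definition in Table 1 with that in Sections 4, 8 and 9.3.3, and state which one governs the strata.
4. State in Section 9.10 that treatment outside the network may be missed, so some patients classed as ALK-inhibitor-naive may be pretreated.

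The cost is an extra column or two in tables already planned, with no new data source. The strata become smaller and the intervals wider. At f = 10% the middle group would be about 15 of 147, or 26 of 260, which is why the two-way split should be the default.
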